### 3.7.4.2 Lipid Measurements

All lipid measurements will be summarized by visit, as well as absolute and percent change from baseline to each post-baseline visit.

The same ANCOVA model as primary efficacy analysis will be used for analyzing the percent change and change:

- From baseline to Week 4,
- From baseline to Week 12 with LOCF (after Day 1 and up to Week 12),
- From baseline to Week 30 with LOCF (after Week 12 and up to Week 30),
- From baseline to Week 36 with LOCF (after Week 12 and up to Week 36),
- Average between Week 30 and Week 36, and
- Average between Week 16 and Week 36

for direct LDL-C, triglycerides, Lp(a), HDL, Non-HDL, Total Cholesterol, Apo C-III (after Week 12 only), and Apo B.

Lp(a) will be analyzed separately for baseline value  $\leq 10$  nmol/L and baseline value  $> 10$  nmol/L. In the ANCOVA model for change from baseline, baseline value will be included as a covariate. But the covariate of baseline value will not be included in the model for the analysis of percent change from baseline.

If skewness from normality is observed for triglycerides data, then the triglycerides value will be logarithm-transformed before fitting the ANCOVA model. The treatment difference between two visits will then be transformed back as the percent change from. If the normality assumption still can't be satisfied with the logarithm-transformed data, a non-parametric approach (Wilcoxon rank-sum test) will be used to compare the difference in median TG change or percent change between treatment groups.

A logistic regression model with treatment as a factor and baseline as a covariate may be used to compare the percentages of patients who achieve a change from baseline to endpoint in Lp(a) ( $\leq 10$  nmol/L vs.  $> 10$  nmol/L) between the MGL-3196 dose versus placebo. The odds ratio, confidence interval, and p-value will be provided.

Analyses of lipids may be performed for the following subgroups:

- Week 12 SHBG group ( $\geq 75\%$ ,  $< 75\%$  change from baseline to Week 12) for men and women separately;
- Week 36 SHBG group ( $\geq 88\%$ ,  $< 88\%$  change from baseline to mean SHBG post Week 12 through Week 36);
- Exposure group (AUC  $< 2700$  ng\*hr/mL, AUC  $\geq 2700$  ng\*hr/mL);
- Baseline Direct LDL Category ( $< 100$  mg/dL,  $\geq 100$  mg/dL);
- Baseline Triglycerides Category ( $\leq 150$  mg/dL,  $> 150$  mg/dL); and
- Any other data driven groups.

### 3.7.4.3 Thyroid Axis Hormones

Summary statistics (number of patients, mean, standard deviation, median, minimum, and maximum) for all visits, including the change and % change from baseline, will be provided for TSH, T4, FT4, T3, FT3, TBG, and Reverse T3 for the mITT population.

The same ANCOVA model will be used for analyzing the percent change and change from baseline to Week 12 for Reverse T3 for the mITT population.

- Sex hormones SHBG, testosterone, free testosterone, LH and FSH will be reported by gender and statistical assessments (CFB, %CFB) at Weeks 12 and 36 provided

### 3.7.4.4 Fibrosis Markers

Fibrosis markers will be assessed by visits based on ITT population. Change and percent change from baseline to Week 12 and Week 36 endpoints will be summarized. The same ANCOVA model will be used for analyzing the change and percent change from baseline to

Week 12 and to Week 36 for fibrosis markers, by overall treatment group, exposure group, and SHBG groups.

Summary and analysis of fibrosis markers will be repeated on all ITT population with Week 12 liver fat reduction  $\geq 30\%$  from baseline in MRI-PDFF for active treatment group vs. all placebo subjects. In addition, the following subgroups will be explored at both Week 12 and Week 36 for each corresponding fibrosis marker:

- Week 12 SHBG group ( $\geq 75\%$ ,  $< 75\%$  change from baseline to Week 12) for men and women separately;
- Week 36 SHBG group ( $\geq 88\%$ ,  $< 88\%$  change from baseline to mean SHBG post Week 12 through Week 36);
- Exposure group (AUC  $< 2700$  ng\*hr/mL, AUC  $\geq 2700$  ng\*hr/mL);
- Baseline ELF  $\geq 9$ ;
- Baseline PIIINP  $\geq 8$   $\mu\text{g}/\text{L}$ ;
- Baseline TIMP  $\geq 129$   $\mu\text{g}/\text{L}$ ;
- Baseline HA  $\geq 50$   $\mu\text{g}/\text{L}$ ; and
- Baseline PRO-C3  $\geq 10$   $\mu\text{g}/\text{L}$ , and  $\geq 17.5$   $\mu\text{g}/\text{L}$ .

For the fibrosis markers (e.g. ELF, pro-C3, adiponectin and CK-18), change from Week 12 to Week 36 will also be summarized and analyzed. This will show durability of response and whether the biomarkers at week 12 is a good a predictor of response or Week 36 is better, and also provide the significance between drug treated and placebo in the change in non-invasive biomarker parameters between Week 12 and Week 36. If there is a significant decrease in ELF and components in the whole population between Weeks 12 and 36 that is larger than the decrease between baseline and Week 12, it might suggest that differences between Week 12 to Week 36 and Week 0 to Week 36 of fibrosis marker data may be used to predict response on liver biopsy.

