Cytokeratin-18, FIB-4, ELF, fibrinogen, haptoglobin, alpha-2 macroglobulin, N-terminal pro b-type natriuretic peptide, apolipoprotein C-III, and ferritin will be measured at the Baseline Visit (Day 1), Week 12, Week 36, and the Early Termination Visit, and Extension Study Day 1, Extension Study Weeks 12 and 36, and the Extension Study Early Termination Visit.

High-sensitivity C-reactive protein will be measured at the Baseline Visit (Day 1), Weeks 4, 12, 24, and 36, and the Early Termination Visit, and Extension Study Day 1, Extension Study Weeks 4, 12, 24, and 36, and the Extension Study Early Termination Visit.

Bone biomarkers Type 1 procollagen N-terminal propeptide and CTX will be measured at the Baseline Visit (Day 1), Main Study Weeks 12 and 36, and the Early Termination Visit, and Extension Study Day 1, Extension Study Weeks 12 and 36, and the Extension Study Early Termination Visit.

Pre-dose PK samples will be drawn at baseline (Day 1), Main Study Weeks 2, 8, 16, 24, and 36, and the Early Termination Visit, and Extension Study Day 1, Extension Study Weeks 2, 4, 8, 16, 24, and 36, and the Extension Study Early Termination Visit. In addition, postdose PK samples will be collected at Main Study Week 2 as described in 6.4.2 and the Extension Study Week 2 as described in 6.7.2.

Coagulation markers (APTT, PT, and INR) will be measured at the Screening Visit (Week -6 to 0), the Baseline Visit (Day 1), Weeks 2, 4, 8, 12, 16, 20, 24, 30, and 36, at the Follow-Up Visit (Week 38), and at the Early Termination Visit, and Extension Study Day 1, Extension Study Weeks 2, 4, 8, 12, 16, 20, 24, 28, 32, and 36 and the Extension Study Early Termination Visit.

Genomic samples will be drawn at the Baseline Visit (Day 1).

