#### 3.7.2.5 Analyses for Week 36 Primary Efficacy Endpoints (MRI-PDFF)

Analyses of hepatic fat fraction from Baseline to Week 36 will follow the same analysis as Week 12, based on the mITT population. This analysis will also be repeated for the 36-Week Per Protocol Population. If there are patients who early withdraw between Weeks 12 and 36, then the following two analyses will be conducted:

- Analyze the primary endpoint (percent or absolute changes in hepatic fat fraction by MRI-PDFF) without the early withdrawals, that is, only include patients who finish Week 36 MRI-PDFF (mITT Population – Observed); and
- Last observation carried forward between Weeks 12 and 36, and use this last observation as the Week 36 value for the analysis (mITT Population – LOCF).

The percent and absolute change in hepatic fat fraction by MRI-PDFF between Week 12 and Week 36 without the early withdrawals will be analyzed, that is, only include patients who finish Week 36 MRI-PDFF. The results between Weeks 12 and 36 will show durability of response and whether MRI-PDFF at week 12 is a good a predictor of response or Week 36 is better.

Additional sensitivity analysis may be performed with other statistical models, such as Mixed effect Model Repeat Measurement (MMRM) method.

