### 3.7.4 Analyses of Other Efficacy Endpoints

Summary statistics (number of patients, mean, standard deviation, median, minimum, and maximum) for all visits, including the change from baseline and percent change from baseline, will be provided for each parameter for the mITT population.

The parameters will be analysed based on the mITT population. For certain efficacy endpoints, such as liver enzymes at Week 12, analysis will be repeated on MRI population as well. Since this is for exploratory purpose, no multiplicity will be controlled. Where stated, the last observation carried forward will be used for missing value imputation when applying an ANCOVA model.

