### **3.7.5 Analyses of Correlation between MRI-PDFF and Other Efficacy Endpoints**

The correlation analyses will be conducted for MGL-3196 and placebo group separately. Both percent change and absolute change from baseline to Week 12 will be used for the correlation analyses.

Spearman's rank correlation coefficient (Spearman's  $\rho$ ) will be used to evaluate the following relationship:

- The correlation between percent change or absolute change in MRI-PDFF and weight loss;
- The correlation between percent change or absolute change in MRI-PDFF and lipid change (percent change or absolute change in direct LDL or triglycerides);
- The correlation between percent change or absolute change in MRI-PDFF and change in ALT;
- The correlation between percent change or absolute change in MRI-PDFF and percent change in SHBG from baseline to Week 12; and
- The correlation in reduction of liver fat on MRI-PDFF at 12 and 36 weeks with improvement or resolution of NASH on liver biopsy.

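### A larger mean fall in fibrosis markers after Week 12 cannot show whether they predict biopsy response, as SAP 3.7.4.4 suggests

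*SAP*

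**What the plan says.** SAP 3.7.4.4 plans to summarise and analyse the change in fibrosis markers (ELF, Pro-C3, adiponectin and CK-18 are given as examples) from Week 12 to Week 36. It attaches two statements about prediction.

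- The analysis will show durability and "whether the biomarkers at week 12 is a good a predictor of response or Week 36 is better". This is stated flatly.
- A condition in two parts follows. One part is a late fall: "If there is a significant decrease in ELF and components in the whole population between Weeks 12 and 36". The other is that this late fall exceeds the one over the first 12 weeks. If both hold, the SAP says, in hedged terms, that differences over time in "fibrosis marker data may be used to predict response on liver biopsy".

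The same paragraph also promises a drug versus placebo comparison of the Week 12 to 36 change.

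For liver fat, SAP 3.7.2.5 contains a similar sentence ("whether MRI-PDFF at week 12 is a good a predictor of response or Week 36 is better"), and SAP 3.7.5 then plans a patient-level analysis, by Spearman's coefficient and separately by arm: "The correlation in reduction of liver fat on MRI-PDFF at 12 and 36 weeks with improvement or resolution of NASH on liver biopsy". No fibrosis marker appears in that list. SAP 3.7.4 sets the status of all the marker work: "Since this is for exploratory purpose, no multiplicity will be controlled".

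**The concern.** A mean change describes the course of a group. Prediction is a statement about patients: those whose marker falls more should be those who improve on biopsy. The two are independent. A marker can fall on average in everyone and be unrelated to histology, or show little mean change and still separate responders from non-responders.

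The stated condition can therefore fail in both directions. It can support a marker that carries no information about biopsy, and pass over one that does. It can also favour the wrong time window. What is at stake is an exploratory conclusion about which marker, read at which week, is worth carrying forward as a stand-in for biopsy. The visits needed to answer that question directly are already scheduled.

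**Working it through.** The plan gives no sample size, power or significance level for this condition, so there is no figure of its own to reproduce.

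**Inputs from the documents**

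- Sampling times: Protocol 9.8 says CK-18, FIB-4 and ELF "will be measured at the Baseline Visit (Day 1), Week 12, Week 36, and the Early Termination Visit". Pro-C3 is not named there; I assume the same visits.
- Patients: the Amendment 6 rationale reports 116 with baseline and Week 12 MRI-PDFF, and the accompanying safety table shows 125. The number with paired biopsies is not given, so 80 to 125 was run.
- Biopsy timing: Protocol 6.4.10 allows 10 days before to 3 days after the Week 36 visit.

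**Assumptions not in the documents:** SD of an individual's change 0.5 in each interval, biopsy response 40%, and the mean falls and correlations shown below.

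**Step 1: interval lengths.** The first interval is 12 weeks and the second is 36 − 12 = 24 weeks. At a constant weekly fall r, the mean falls are 12r and 24r, a ratio of 2. The late fall is the larger in expectation, with no reference to histology. The SAP states no per-week adjustment.

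**Step 2: approximate chance that the late mean exceeds the early mean.** With n patients and uncorrelated changes, the SE of the difference between the two means is 0.5 × √(2/n). For n = 116 this is 0.0657.

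- Falls 0.10 then 0.20: z = 0.10/0.0657 = 1.52, probability about 0.94.
- Falls 0.15 then 0.30: z = 0.15/0.0657 = 2.28, probability about 0.99.

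**Step 3: simulation,** 4000 trials per scenario. The condition was coded as a mean Week 12 to 36 fall significant at two-sided 0.05 and larger than the mean Week 0 to 12 fall. Correlation means that between a patient's marker fall and that patient's underlying histological improvement.

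| Scenario | Mean falls (early, late) | Correlation with histology | Condition met, n = 116 | Range, n = 80 to 125 | AUROC of marker change |
|---|---|---|---|---|---|
| A, constant rate | 0.15, 0.30 | none | 99.1% | 97.1–99.2% | 0.50 |
| A, slower | 0.10, 0.20 | none | 92.9% | 86.8–94.5% | 0.50 |
| B, early fall | 0.30, 0.10 | 0.6, both intervals | 0.0% | at most 0.03% | 0.78 each interval; 0.85 for Weeks 0–36 |
| C, no mean fall | 0, 0 | 0.6, both intervals | 2.5% | 2.2–2.5% | 0.78 each interval; 0.85 for Weeks 0–36 |
| D, late fall | 0.10, 0.30 | 0.6 early only | 99.9% | 99.3–99.9% | 0.78 early; 0.50 late |

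The condition is nearly always met by a marker with no link to biopsy (A) and almost never by a predictive one (B, C). In D it is met because of the interval that carries no information.

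**Step 4: a second set of assumptions.** With 110 patients, 30% responders and SD 0.5, an unrelated marker falling 0.05 then 0.20 met the condition in 97% of trials. A predictive marker (AUROC 0.79) falling 0.25 then 0.10 met it in 1%, and the same marker with equal falls in 50%. Letting early and late changes correlate at −0.3 gives 97%, 3% and 51%.

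**Step 5: is the link made elsewhere?** SAP 2.1.3, 2.3.1.2, 2.3.1.3, 3.7.3 and 3.7.5 each name liver fat on MRI-PDFF against biopsy. None of their readable text names ELF, Pro-C3 or CK-18 against biopsy.

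**The case against.** Several points can be made for the plan, and most limit the finding without removing it.

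- **It is not a decision rule.** The sentence about a larger late fall is hedged, sets no threshold, triggers no action and sits in a section declared exploratory. A reader might infer that the SAP will formally declare markers predictive on this basis; the text does not say so. The sentence on which week predicts better is unhedged, however, and has the same flaw.
- **Pooling of arms.** A reader might take the reference to the whole population as drug and placebo combined. That is one reading. The phrase follows a list of subgroups and may mean only that no subgroup is selected, and the paragraph also promises a drug versus placebo comparison. The flaw does not depend on which reading is right.
- **SAP 3.7.2.5.** A reader might extend the criticism to MRI-PDFF. That section has no condition about a larger late fall, and SAP 3.7.5 already relates liver fat reduction to biopsy patient by patient. SAP 3.7.3 also analyses biopsy results in drug-treated patients who reached MRI-PDFF thresholds, against all placebo patients. No new analysis is needed there.
- **Is prediction an aim of the trial?** The readable marker objective (SAP 2.1.2) is the drug's effect on the markers. Exploratory objectives in Protocol 2.3 and SAP 2.1.4 and 2.1.5, and some biopsy items, are blacked out. A marker versus biopsy analysis could be listed there, so one cannot say that the plan contains none. The question of prediction is nevertheless raised by 3.7.4.4 itself.
- **The percentages depend on the coding.** The SAP speaks of ELF and its components. If four markers with equal falls and between-marker correlation 0.3 to 0.7 must all meet the condition, the Step 4 figure of about 97% drops to 89–94%, the 50% drops to 14–27%, and the 1% stays near zero. The direction stands.

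**Conclusion.** The two predictive inferences in SAP 3.7.4.4 do not follow from the analyses described there. Mean change before and after Week 12 carries no information on whether a marker predicts biopsy response, and comparing a 12-week with a 24-week interval tilts the condition towards being met. At 116 patients, under the assumed values, a marker unrelated to biopsy met it in 93% to 99% of trials (87% to 99% over 80 to 125 patients), while a predictive marker that fell early met it in at most 0.03%. These figures are illustrations: the mean falls, SD, response rate and correlations are assumed. The interval arithmetic and the logical gap need no such assumptions.

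The consequence is confined to exploratory interpretation. The primary Week 12 MRI-PDFF analysis and the biopsy responder comparisons do not depend on it. The statement that no marker versus biopsy analysis exists holds only for the readable text.

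**What to change.** - In SAP 3.7.4.4, delete both predictive inferences. Keep the Week 12 to 36 mean change as a durability summary with its drug versus placebo comparison.
- Add the fibrosis markers to the patient-level biopsy analyses in SAP 3.7.5. In patients with both biopsies, relate each marker's change from baseline to Week 12 and, separately, to Week 36 to three responses the SAP already defines: 2-point NAS reduction, NASH resolution, and fibrosis reduction of at least one stage.
- Use Spearman correlation within arm, as for MRI-PDFF. Add the AUROC of the marker change itself, within or stratified by arm, with a 95% CI and the paired Week 12 versus Week 36 difference in the same patients. Do not use the AUROC of a model containing treatment, which would credit the treatment effect to the marker.
- Describe the Week 36 result as concurrent association, because the biopsy belongs to the same visit.
- In SAP 3.7.2.5, let the sentence on prediction refer to 3.7.5.

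The cost is SAP wording and a few exploratory analyses on assessments already scheduled. The drawback is wide intervals. By the Hanley–McNeil formula with 33 responders and 77 non-responders (30% of 110, assumed), the SE of a single AUROC is 0.060 at 0.5 and 0.050 at 0.8, so the 95% CI is about ±0.10 to ±0.12 (1.96 × SE). Within one arm it will be wider.

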### 3.7.4.5 Other Efficacy Variables

Other efficacy variables will also be summarized as appropriate. These efficacy variables include: Direct and Total Bilirubin, ALP, fibrinogen, hsCRP, weight, BMI, eGFR, Troponin I, HR-QoL SF-36 scores, HOMA-IR, HbA1c, NEFA, adipo-IR, adiponectin, Haptoglobin, waist circumference, waist-hip ratio, and blood pressure.

Change or percent change from baseline to Week 12 and Week 36 endpoints will be summarized. For certain endpoints, Mixed Model for Repeated Measurements (MMRM) will also be used to test the robustness of the results. The MMRM analysis does not impute any missing values. For all endpoints, the active MGL-3196 doses will be grouped into one to be compared with placebo.

In the evaluations of insulin resistance parameters such as glucose, HgbA1C, insulin, HOMA-IR, any other calculated insulin resistance indices, any diabetic patients or patients on diabetes medicines will be excluded, since these parameters are known to be confounded with anti-diabetic treatment. However, this rule will not be applicable to the assessment of adiponectin.

### **3.7.5 Analyses of Correlation between MRI-PDFF and Other Efficacy Endpoints**

The correlation analyses will be conducted for MGL-3196 and placebo group separately. Both percent change and absolute change from baseline to Week 12 will be used for the correlation analyses.

Spearman's rank correlation coefficient (Spearman's  $\rho$ ) will be used to evaluate the following relationship:

- The correlation between percent change or absolute change in MRI-PDFF and weight loss;
- The correlation between percent change or absolute change in MRI-PDFF and lipid change (percent change or absolute change in direct LDL or triglycerides);
- The correlation between percent change or absolute change in MRI-PDFF and change in ALT;
- The correlation between percent change or absolute change in MRI-PDFF and percent change in SHBG from baseline to Week 12; and
- The correlation in reduction of liver fat on MRI-PDFF at 12 and 36 weeks with improvement or resolution of NASH on liver biopsy.

### **3.7.6 Analyses of Correlation between MGL-3196 Exposure and Efficacy Endpoints**

Analyses will also be conducted to investigate the correlation between MGL-3196 exposure with efficacy and safety endpoints.

## **3.8 Analysis of Safety**

The safety endpoints for this study include: AEs, safety laboratory assessments, vital signs, 12-lead ECGs, bone mineral density by Dexa scan, and clinical assessments. The safety endpoints will be summarized based on the Safety Population.

### **3.8.1 Adverse Events**

A Treatment-Emergent Adverse Event (TEAE) is defined as any AE that occurred for the first time after the first dose of double-blind study drug or existed prior to the first dose and worsened during the post dosing period. AE worsening applies to severity, or relationship to study drug.

A summary overview of TEAEs will be provided, which presents the number and percentage of patients in each treatment group from the Safety Population for the 12-week Treatment Period and the whole 36-week Treatment Period satisfying each of the following categories:

- Any TEAEs,
- Maximum severity of TEAEs,
- Study drug-related TEAEs,
- Maximum severity of study drug-related TEAEs,
- All TE-SAEs,
- All study drug-related TE-SAEs,
- TEAEs leading to death,
- TEAEs leading to study drug discontinuation, and
- Study drug-related TEAEs leading to interruption/study drug discontinuation.

Adverse events will be coded using MedDRA. The number and percentage of patients with TEAEs will be summarized by their MedDRA preferred term within system organ class and by treatment. AEs will be counted by the number of events as well as the number of patients. For event count summaries, multiple AE events with the same MedDRA coded terms (preferred term and system organ class) and onset date and time from the same patient will only be counted once. For patient count summaries, multiple AE events with the same MedDRA coded terms (preferred term and system organ class) from the same patient will only be counted once. Whether the AE belongs to the 12-week Treatment Period and the whole 36-week Treatment Period will be determined by the AE onset date.

The number and percentage of patients with TEAEs will be summarized by reported maximum severity within each MedDRA preferred term within system organ class and by treatment.

The number and percentage of patients with any TE-SAEs, drug-related TEAEs, drug-related TE-SAEs, and TEAEs and TE-SAEs that lead to study drug discontinuation will be summarized by preferred term within system organ class and by treatment. In these summaries, any patients reporting multiple episodes of the same TEAE (i.e., same preferred term and system organ class) will be counted once.

All SAEs will be listed with an indication of whether the SAE was treatment emergent or started prior to treatment.

All TEAEs that are reported as having led to a withdrawal of study drug will be listed.

